4.2 Number of Subjects

Approximately 60 subjects will be enrolled in the study, with up to 20 subjects to be enrolled in the dose exploration phase (Part 1) and 40 subjects to be enrolled in the dose expansion phase (Part 2). Based on emerging data in Part 2, the protocol may be amended to increase the sample size.

Subjects in this clinical investigation shall be referred to as “subjects”. For the sample size justification, see Section 9.2.

4.2.1 Replacement of Subjects

If a subject stops or delays treatment for more than 72 hours for reasons other than DLT during the DLT evaluation period, a replacement subject may be enrolled and assigned to the same dose level.

4.2.2 Number of Sites

Approximately 25 investigative sites in the US, Europe, and Australia will be included in the study. Sites that do not enroll subjects within 4 months of site initiation may be closed.

4.3 Justification for Investigational Product Dose

The selection of the tarlatamab dose and dosing schedule for this study, which includes the number of dose steps (run-in and step doses) will be based on the dose levels that have been deemed safe and tolerable by the DLRT in the ongoing first-in human (Study 20160323). It is anticipated that the selected regimen will demonstrate a comparable safety and tolerability profile to that determined in subjects in SCLC. In addition, the selected regimen is expected to show clinical activity in subjects with NEPC based on the preliminary evidence of efficacy in subjects with SCLC.

Based on Study 20160323, it is expected that the selected regimen will include step dosing (run-in dose on cycle 1 day 1 followed by 1 [REDACTED] escalating doses to reach a target dose) during cycle 1, followed by the target dose every 2 weeks thereafter. The step-dosing approach has been implemented to mitigate the risk of cytokine release syndrome. The potential doses of tarlatamab to be used for run-in, step or target doses include [REDACTED] mg (or intermediate dose levels), which are under evaluation in Study 20160323.

4.4 End of Study

4.4.1 End of Study Definition

Primary Completion: The primary completion date is defined as the date when the last subject is assessed or receives an intervention for the final collection of data for the primary endpoint(s).

If the study concludes prior to the primary completion date originally planned in the protocol (ie, early termination of the study), then the primary completion will be the date when the last subject is assessed or receives an intervention for evaluation in the study (ie, last subject last visit).

End of Study: The end of study date is defined as the date when the last subject across all sites is assessed or receives an intervention for evaluation in the study (ie, last subject last visit), following any additional parts in the study (eg, long-term follow-up, [REDACTED]), as applicable.

Amgen will not continue provision of investigational product for subjects after their study participation ends unless it is a legal requirement.

4.4.2 Study Duration for Subjects

The study duration for subjects will be approximately up to 3 years. The study duration will consist of up to 28 days for screening, a variable period on treatment (depending on

the subject's response), and a safety follow-up (SFU) period of up to approximately 60 days (+5 days) after the last dose of tarlatamab. For all subjects who have not withdrawn consent, long-term follow-up assessment will also be conducted every 3 months up to 3 years from the first dose of tarlatamab by clinic visit, telephone or chart review to assess for survival and/or the commencement of subsequent cancer therapy.

4.5 Patient Input on Study Design

Patient input was not obtained on study design.

5. Study Population

Investigators will be expected to maintain a screening log of all potential study candidates that includes limited information about the potential candidate (eg, date of screening).

Eligibility criteria will be evaluated during screening.

Before any study-specific activities/procedures, the appropriate written informed consent must be obtained (see Section 11.3).

Prospective approval of protocol deviations to recruitment and enrollment criteria, also known as protocol waivers or exemptions will not be provided.

5.1 Inclusion Criteria

Subjects are eligible to be included in the study only if all of the following criteria apply:

- 101 Subject has provided informed consent prior to initiation of any study specific activities/procedures.
- 102 Men aged ≥ 18 years at time of signing the informed consent.
- 103 Metastatic de novo or treatment-emergent neuroendocrine prostate cancer (NEPC) defined as one or more of the following:
 - Histological diagnosis of small cell NEPC
 - Histologic evidence of prostate cancer with neuroendocrine differentiation as defined by positive immunohistochemical staining for chromogranin and/or synaptophysin in the majority of the tumor sample
 - ≥ 2 alterations in Tp53, RB1, and/or PTEN by immunohistochemistry (IHC) or genomic analyses of baseline tumor tissue (by local assessment) or ██████████ (by local assessment). Tp53 by IHC is considered abnormal if $\geq 10\%$ tumor nuclei showed positive staining. RB1 and PTEN by IHC is considered abnormal if $\leq 10\%$ tumor cells showed positive staining. On genomic analyses, nonsynonymous missense or stop-gain mutations, frameshift or non-frameshift indels (insertions and deletions), and/or copy number losses in ≥ 2 of Tp53, RB1, and PTEN is considered abnormal.

- 104 At least 1 line of prior systemic treatment, including a platinum containing regimen for de novo neuroendocrine prostate cancer (if at the time of NEPC diagnosis they had no prior diagnosis or treatment for prostate carcinoma) or an androgen signaling inhibitor (eg, abiraterone, enzalutamide, darolutamide and/or apalutamide) if treatment-emergent (had a previous diagnosis of prostate carcinoma prior to NEPC diagnosis).
- Exception: Subjects may also be included if the aforementioned therapeutic options were medically not appropriate for them.
- 105 For subjects with treatment-emergent NEPC or de novo NEPC with histologic evidence of prostate cancer with neuroendocrine differentiation as defined by positive immunohistochemical staining for chromogranin and/or synaptophysin in the majority of the tumor sample (unless refractory to prior androgen deprivation treatment), a total serum testosterone of ≤ 50 ng/dl or 1.7 nmol/L
- 106 Subjects with treatment-emergent NEPC or de novo NEPC with histologic evidence of prostate cancer with neuroendocrine differentiation as defined by positive immunohistochemical staining for chromogranin and/or synaptophysin in the majority of the tumor sample (unless refractory to prior androgen deprivation treatment), without a history of bilateral orchiectomy, are required to remain on luteinizing hormone-releasing hormone (LHRH) analogue therapy during the course of protocol therapy
- 107 Measurable disease per Response Evaluation Criteria in Solid Tumors (RECIST) 1.1 per Prostate Cancer Working Group 3 (PCWG3) modifications (Sections 11.8 and 11.9)
- 108 Eastern Cooperative Oncology Group (ECOG) Performance Status of ≤ 2
- 109 Life expectancy of > 3 months, in the opinion of the investigator
- 110 Subjects with treated brain metastases are eligible provided they meet the following criteria:
- Definitive treatment was completed at least 2 weeks prior to the first planned dose of study treatment (stereotactic radiosurgery at least 7 days prior to first planned dose of study treatment)
 - At least 7 days prior to treatment: any central nervous system (CNS) disease is clinically stable, subject is off steroids for CNS disease (unless steroids are indicated for a reason unrelated to CNS disease), and subject is off or on stable doses of anti-epileptic drugs.
- 111 Adequate organ function, defined as follows:
- Adequate hematological laboratory assessments, as follows:
- Absolute neutrophil count (ANC) $\geq 1 \times 10^9/L$
 - Platelet count $\geq 75 \times 10^9/L$
 - Hemoglobin ≥ 9 g/dL
- Adequate renal laboratory assessments, as follows:

- Estimated glomerular filtration rate based on Modification of Diet in Renal Disease (MDRD) calculation ≥ 30 mL/min/1.73 m²

Adequate hepatic laboratory assessments, as follows:

- Aspartate aminotransferase (AST) < 3 x upper limit of normal (ULN) (if liver metastases are present, ≤ 5 x ULN)
- Alanine aminotransferase (ALT) < 3 x ULN (if liver metastases are present, ≤ 5 x ULN)
- Total bilirubin (BIL) < 1.5 x ULN (< 2.0 x ULN for subjects with liver metastases)

Adequate coagulation laboratory assessments, as follows:

- Prothrombin time/international normalized ratio (PT/INR) and partial thromboplastin time (PTT) or activated partial thromboplastin time (APTT) ≤ 1.5 x institutional ULN. Subjects on chronic anticoagulation therapy who do not meet the criteria above may be eligible to enroll after discussion with the medical monitor.

Cardiac function:

- Cardiac ejection fraction $\geq 50\%$
- No clinically significant electrocardiogram (ECG) findings

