Approximately 60 subjects will be enrolled in this study. Up to 20 subjects will be enrolled in the dose exploration phase (Part 1) and 40 subjects will be enrolled in the dose expansion phase (Part 2). Based on emerging data in Part 2, the protocol may be amended to increase the sample size.

Summary of Subject Eligibility Criteria

Adult subjects (≥ 18 years of age) with metastatic de novo or treatment-emergent NEPC defined as one or more of the following will be eligible to enroll: histological diagnosis of small cell NEPC, prostate carcinoma with neuroendocrine differentiation as defined by positive immunohistochemical staining for chromogranin and/or synaptophysin in the majority of the tumor sample or ≥ 2 alterations in Tp53, RB1, and/or PTEN by immunohistochemistry (IHC) or genomic analyses of baseline tumor tissue of [REDACTED]

[REDACTED] Subjects are required to have progressed on at least 1 line of prior treatment, including a platinum containing regimen for de novo NEPC (if at the time of NEPC diagnosis they had no prior diagnosis or treatment for prostate carcinoma) or an androgen signaling inhibitor (eg, abiraterone, enzalutamide, and/or apalutamide) if treatment-emergent (had a previous diagnosis of prostate carcinoma prior to NEPC diagnosis). Subjects must have measurable disease per Response Evaluation Criteria in Solid Tumors (RECIST) 1.1 criteria with Prostate Cancer Working Group 3 (PCWG3) guidelines, have an Eastern Cooperative Oncology Group (ECOG) performance status of ≤ 2 , and adequate organ function.

For a full list of eligibility criteria, please refer to Section 5.1 to Section 5.2.

Treatments

Tarlatamab is an Amgen investigational product used in this study. Tarlatamab will be manufactured and packaged by Amgen Inc. and distributed using Amgen clinical study drug distribution procedures.

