^a Results of imaging assessments conducted as standard of care may be use for screening within 30 days of start of study treatment.

^b Timing is based on first dose of Tarlatamab (cycle 1 day 1) ± 7 days for imaging assessments.

^c Per PCWG3 recommendations, the first post-treatment bone scan (at week 8) will be used as the baseline scan with which all future bone scans are compared.

^d Radiologic imaging and tumor assessments are required at screening and every 8 ± 1 weeks post-therapy initiation until clinically significant disease progression or deterioration, withdrawal of consent or start of new anticancer therapy. Every assessment must include the chest, abdomen, and pelvis, all other known sites of disease and MRI of the brain if a subject has signs or symptoms suggestive of CNS metastases. The MRI/CT can be obtained earlier if clinical deterioration necessitates an earlier scan at the discretion of the managing physician. The same contrast and modality used at screening should be used for all subsequent assessments. ^{99m}Tc-MDP bone scan is required for each radiologic imaging and tumor assessment. Tumor burden assessments will be performed based on PCWG3 guidelines (Sections 11.8 and 11.9). To confirm soft tissue disease progression, a second MRI/CT scan must be performed at least 4 weeks after the first detection of soft tissue disease progression. Confirmation of bone disease progression by bone scan should be performed per PCWG3 guidelines. Responses require confirmation by a repeat consecutive assessment at least 4 weeks after the first detection of response as measured by RECIST 1.1.

^e For subjects who discontinued treatment for any reason other than confirmed PD, every effort should be made to perform radiographic imaging (CT/MRI/bone) of the chest, abdomen, pelvis, bone, and all other known sites of disease every 3 months until documentation of confirmed PD per PCWG3 guidelines, clinical progression, start of new anticancer therapy, or up to 3 years after the first dose of tarlatamab, whichever occurs first.

2. Introduction

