4.1 Overall Design

This is an open label phase 1b study evaluating tarlatamab monotherapy.

[figure not shown]
Tarlatamab will be administered as a short-term IV infusion Q2W (with step dosing) in a 28-day cycle as monotherapy therapy in subjects with de novo or treatment-emergent NEPC.

The study will consist of 2 parts: dose exploration (Part 1) and dose expansion (Part 2).

Dose Exploration (Part 1)

The dose exploration part of the study will enroll up to 20 subjects with relapsed/refractory (RR) NEPC. At the time of initiation of the study, the starting dose will be the highest dose deemed safe and tolerable in the ongoing phase 1 trial of tarlatamab in subjects with small cell lung cancer (Note: based on emerging safety data

from Study 20160323, the starting dose may be lower than the highest dose deemed safe and tolerable). The planned highest dose in this study is not anticipated to exceed the maximum tolerated dose (MTD) as established in the ongoing Study 20160323. Based on results from study 20160323 in small cell lung cancer, the doses that may be explored in this study are presented in [Table 4-1](#).

Due to its known mechanism of action, subjects are at an increased risk for first dose effects (eg, CRS with associated manifestations and any other potentially evolving and unknown first dose effects) following the initial infusion of tarlatamab. To mitigate these risks, a step dosing approach will be implemented. One of the following step dosing approaches will be utilized as the initial dosing schedule based on emerging data and the dosing schedule associated with the highest dose deemed safe and tolerable from the ongoing first-in-human (FIH) study (Note: based on emerging safety data from Study 20160323, the starting dose may be lower than the highest dose deemed safe and tolerable).

- Single-step dosing involving a run-in dose on day 1, followed by a step dose on day 8 (equal to the target dose) and the target dose on day 15 then Q2W.

Based on emerging safety, pharmacokinetic and pharmacodynamic data from this study as well as the ongoing FIH study (20160323) and the recommendations of the DLRT, multiple or parallel dosing cohorts may also be opened simultaneously to assess any of the step-dosing strategies as described above.

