- Note: Simple UTI and uncomplicated bacterial pharyngitis are permitted if responding to active treatment and after consultation with sponsor. Subjects requiring oral antibiotics who have been afebrile > 24 hours, have no leukocytosis or have any clinical signs of infection are eligible. Subjects who meet these criteria and who were previously on IV antimicrobials should have been off IV antimicrobials for > 48 hours.
- 210 Exclusion of hepatitis infection based on the following results and/or criteria:
- Positive Hepatitis B Surface Antigen (HepBsAg) (indicative of chronic Hepatitis B or recent acute hepatitis B).
 - Negative HepBsAg and positive for hepatitis B core antibody: hepatitis B virus DNA by polymerase chain reaction (PCR) is necessary. Detectable hepatitis B virus DNA suggests occult hepatitis B.
 - Positive Hepatitis C virus antibody: Hepatitis C virus RNA by PCR is necessary. Detectable Hepatitis C virus RNA suggests chronic hepatitis C.
- 211 Known positive test for human immunodeficiency virus (HIV)
- 212 Anti-tumor therapy within 28 days of study day 1; concurrent use of hormone deprivation therapy for hormone-refractory prostate is permitted; subjects on a stable bisphosphonate or denosumab for ≥ 30 days prior to study day 1 are eligible
- Exceptions:
 - Subjects who received conventional chemotherapy are eligible if at least 14 days have elapsed and if all treatment-related toxicities have resolved to Grade ≤ 1
 - Prior palliative radiotherapy must have been completed at least 7 days before the first dose of tarlatamab
 - Subjects who received androgen signaling inhibitor (eg, abiraterone, enzalutamide, and/or apalutamide) are eligible if at least 14 days have elapsed and if all treatment-related toxicity has been resolved to Grade ≤ 1
- 213 Major surgical procedures ≤ 28 days or non–study-related minor procedures ≤ 7 days prior to study day 1. In all cases, the subjects must be sufficiently recovered and stable before treatment administration

- 214 Currently receiving treatment in another investigational device or drug study, or less than 28 days **from study day 1** since ending treatment on another investigational device or drug study(ies). Other investigational procedures while participating in this study are excluded with the exception of

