11.8 Appendix 8. Response Evaluation Criteria in Solid Tumors Version 1.1 (RECIST v1.1)

Definitions

- Measurable Lesions
 - Measurable Tumor Lesions – Non-nodal lesions with clear borders that can be accurately measured in at least 1 dimension with longest diameter ≥ 10 mm in computed tomography/magnetic resonance imaging (CT/MRI) scan with slice thickness no greater than 5 mm. When slice thickness is greater than 5 mm, the minimum size of measurable lesion should be twice the slice thickness.
 - Nodal Lesions - Lymph nodes are to be considered pathologically enlarged and measurable, a lymph node must be ≥ 15 mm in short axis when assessed by CT/MRI (scan slice thickness recommended to be no greater than 5 mm). At baseline and in follow-up, only the short axis will be measured and followed.
 - Nodal size is normally reported as two dimensions in the axial plane. The smaller of these measures is the short axis (perpendicular to the longest axis).
 - Irradiated Lesions - Tumor lesions situated in a previously irradiated area, or in an area subjected to other loco-regional therapy, are not measurable unless there has been demonstrated progression in the lesion prior to enrollment.
- Non-measurable Lesions
 - All other lesions, including small lesions (longest diameter < 10 mm or pathological lymph nodes with ≥ 10 mm but to < 15 mm short axis with CT scan slice thickness no greater than 5 mm) are considered non-measurable and characterized as non-target lesions.
 - Other examples of non-measurable lesions include:
 - Lesions with prior local treatment: tumor lesions situated in a previously irradiated area, or an area subject to other loco-regional therapy, should not be considered measurable unless there has been demonstrated progression in the lesion.
 - Biopsied lesions
 - Categorially, clusters of small lesions, bone lesions, inflammatory breast disease, and leptomeningeal disease are non-measurable.

Methods of Measurement

- Measurement of Lesions - The longest diameter of selected lesions should be measured in the plane in which the images were acquired (axial plane). All measurements should be taken and recorded in metric notation. All baseline evaluations should be performed as closely as possible to the beginning of treatment and not more than 4 weeks before study day 1.
- Methods of Assessment - The same method of assessment and the same technique should be used to characterize each identified and reported lesion throughout the trial.

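### The synopsis and criterion 104 disagree on prior progression, and the RECIST baseline scan may predate the last prior therapy, so shrinkage from that therapy can be counted as tarlatamab response

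*Protocol*

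**What the plan says.** **Prior treatment.** The synopsis (Protocol Section 1.1) states: "Subjects are required to have progressed on at least 1 line of prior treatment, including a platinum containing regimen for de novo NEPC". Criterion 104 (Section 5.1) asks for "At least 1 line of prior systemic treatment, including a platinum containing regimen for de novo neuroendocrine prostate cancer", or an androgen signaling inhibitor for treatment-emergent disease. It adds an exception that the synopsis lacks: "Subjects may also be included if the aforementioned therapeutic options were medically not appropriate for them". No other criterion in Sections 5.1 or 5.2 requires progression. Criterion 107 requires measurable disease only. Section 4.1 says that Part 1 "will enroll up to 20 subjects with relapsed/refractory (RR) NEPC"; this describes the population, is not an eligibility criterion, and is not repeated for Part 2.

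**Interval since prior therapy.** Exclusion 212 bars anti-tumor therapy within 28 days of day 1, with exceptions. One reads "Subjects who received conventional chemotherapy are eligible if at least 14 days have elapsed"; another reads "Subjects who received androgen signaling inhibitor (eg, abiraterone, enzalutamide, and/or apalutamide) are eligible if at least 14 days have elapsed". Both also require treatment-related toxicity to have resolved to Grade 1 or lower.

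**Age of the baseline scan.** The general screening window is 28 days (footnote a to Tables 1-1 and 1-2). Table 1-3 footnote a says: "Results of imaging assessments conducted as standard of care may be use for screening within 30 days of start of study treatment". Appendix 8 (Section 11.8) wants baseline evaluations close to the start of treatment and "not more than 4 weeks before study day 1". None of these ties the scan to the last dose of prior therapy. SAP Section 5.1 takes the last value before the first tarlatamab dose as baseline, again with no such tie. Appendix 8 measures partial response as a decrease of at least 30% from the baseline sum of diameters.

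**The concern.** OR, DCR and DOR come from a single arm with no control. Reading a response as tarlatamab activity relies on the reference scan showing the tumour after other active therapy has stopped. If a cycle of chemotherapy falls between the reference scan and day 1, the change measured at week 8 combines the effect of that cycle with the effect of tarlatamab, and the response rules credit all of it to tarlatamab. The same count feeds the Bayesian futility rule in Part 2.

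The disagreement over progression bears on this. A tumour progressing through its last therapy is unlikely to shrink later because of it; a tumour still responding may. Under criterion 104 a subject still responding to a first line of platinum is eligible. Under the synopsis that subject is not.

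**Working it through.** **Step 1. Eligibility texts side by side.**

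| Item | Synopsis | Criterion 104 |
|---|---|---|
| At least 1 prior line | yes | yes |
| Progression on that line | required | not mentioned |
| Exception if options not medically appropriate | absent | present |
| Darolutamide among the examples | absent | present |

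The texts differ in both directions, so neither is simply a shortened copy of the other. The synopsis refers to Sections 5.1 and 5.2 for the full list, so sites would apply criterion 104.

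**Step 2. Dates.** Longest period of prior therapy after the scan = maximum scan age − minimum interval since last dose.

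- 28-day window: 28 − 14 = 14 days.
- 30-day standard-of-care window: 30 − 14 = 16 days.
- 4-week limit in Appendix 8: 28 − 14 = 14 days.

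Example: scan on day −28, chemotherapy on day −14, tarlatamab on day 1. The timing rules allow this, provided toxicity has resolved to Grade 1 or lower and the organ-function limits are met.

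**Step 3. Reproduce the plan's ORR figures.** Inputs from Protocol Sections 9.2 and 9.4.1.1: n = 40, Beta(1,1) prior, target 30%, NoGo if P(ORR > 30%) < 5%, futility if the predictive probability of NoGo exceeds 95%, looks at 20 and 30, final at 40.

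- Clopper-Pearson interval for 8/40: 9.1% to 35.6% (stated 9% to 36%).
- NoGo: P(ORR > 0.30 | x of 40) is the upper tail of Beta(1+x, 41−x) at 0.30. It is 0.046 at x = 7 and 0.094 at x = 8, so NoGo means 7 or fewer.
- Futility after m subjects with x responders: P(Y ≤ 7−x), with Y beta-binomial(40−m, 1+x, 1+m−x). At m = 20 this is 0.982 for x = 1 and 0.897 for x = 2. At m = 30 it is 0.987 for x = 3 and 0.918 for x = 4. The limits are 1 of 20 and 3 of 30; the second matches the protocol's example.
- Probability of futility at true ORR 10/15/20/25/30/35/40%: 95.9/76.0/44.5/18.8/5.9/1.4/0.3% (Table 9-3: 96/76/44/19/6/1/0%).

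**Step 4. Effect of one subject.** At each limit one extra counted responder reverses the result: 1 to 2 of 20, 3 to 4 of 30, 7 to 8 of 40.

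**Step 5. Range under stated assumptions.** Let f be the share of subjects with carry-over exposure and g the chance that an exposed subject who would not respond to tarlatamab is still counted as a responder. The documents give neither. With true ORR at the 12% benchmark, counted ORR = 0.12 + 0.88 × f × g.

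| f | g | Counted ORR | P(futility or NoGo) |
|---|---|---|---|
| 0 | – | 12.0% | 90% |
| 10% | 10% | 12.9% | 87% |
| 10% | 20% | 13.8% | 83% |
| 20% | 30% | 17.3% | 62% |
| 30% | 30% | 19.9% | 45% |

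The last column includes the looks at 20 and 30. One value of g is used throughout, although interim looks count unconfirmed responses and the final analysis does not. The table shows sensitivity; it is not an estimate.

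**The case against.** Several points on the other side stand.

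- A reader might infer that criterion 104 lost the progression requirement by mistake. The documents do not show this. Criterion 104 holds details that the synopsis lacks, so it may be the later text. They support only that the two must be reconciled.
- The synopsis asks for progression on at least one line, not the most recent. A subject who progressed on a first line and is responding to a later one satisfies both texts, so reconciling them does not by itself close the scan gap.
- The Grade 1 toxicity condition and the blood-count limits in criterion 111 narrow the group of such subjects. They do not empty it.
- Final responses need confirmation at least 4 weeks later. With a scan at week 8, carry-over would have to persist to about 2 + 8 + 4 = 14 weeks after the last chemotherapy dose. That argues for a small g at the final analysis. It does not remove the problem: confirmation against the same early baseline confirms any shrinkage that lasts, and interim looks also count unconfirmed responses.
- Where a tumour grew between the scan and day 1, an early baseline works against tarlatamab, so the bias is not upward in every subject.
- The protocol associates NEPC with loss of dependence on androgen signaling, which makes carry-over from those inhibitors less plausible than from chemotherapy.
- An imaging manual, which is not among the documents, may order the scan after the last dose.

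The Appendix 8 rule on irradiated lesions covers local therapy only and does not answer the point about systemic therapy.

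**Conclusion.** Two things hold on the text alone. The synopsis and criterion 104 disagree on whether progression is required. The RECIST baseline may predate up to 14 to 16 days of prior therapy, so shrinkage from that therapy can enter ORR, DCR, DOR and the futility count.

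The size of the effect cannot be derived, because the number of such subjects and their response rate are both assumptions. What can be said is that a single such responder matters at the limits. The NoGo criterion serves interim futility only, and the futility rule is non-binding. Efficacy is secondary, no hypothesis is tested, and the safety and DLT objectives are untouched.

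A reader might go further and infer that the trial cannot tell tarlatamab activity from carry-over. The documents do not support that. Section 6.7.1 collects start and stop dates, type of progression and resistant or sensitive status for prior prostate cancer therapies, so affected subjects can be identified. The unredacted text, however, plans no analysis that uses these data for this purpose.

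**What to change.** 1. Reconcile the synopsis with criterion 104, so that both state the same position on progression and the same exception. Which position to take is for the sponsor.
2. In Table 1-3 footnote a and Appendix 8, require the RECIST baseline scan to be acquired after the last dose of prior anticancer therapy, and give one outer limit in place of 30 days and 4 weeks. State that therapy allowed to continue on study (the LHRH analogue under criterion 106, and hormone deprivation under exclusion 212) is outside this rule. The period of prior therapy after the scan then becomes 0 days.
3. For subjects already enrolled, add to the SAP a sensitivity ORR from the Section 6.7.1 dates. Subjects whose baseline scan predates the last prior dose stay in the denominator and are not counted as responders. This is deliberately conservative, since some of them may have truly responded to tarlatamab.

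The cost is amendment wording and one extra SAP table. A few standard-of-care scans could not be reused, and for those subjects the screening scan is done later. No change to the washout intervals is proposed.
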